3.2 Endpoints

The primary outcome is the change in abdominal aortic aneurysm maximum transverse diameter (MTD) on CT scan from baseline to the follow-up assessment CT scan two years after randomization, as measured in the Imaging Core Laboratory (ICL).

Secondary outcomes will derive from central ICL analyses of the CT scans performed every six months on patients and from the clinical follow-up of randomized patients, from clinical observation, local laboratory findings, study visit quality of life assessments, and from biomarker analyses to be performed in the Biomarkers Core Laboratory (e.g., changes from initial MMP-9 levels, and MMP-9 levels at 24 months of follow-up).

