4.1.2 Full Analysis Population

The full analysis population includes all patients randomized except those with no follow-up contact and no follow-up CT scan, analyzed by treatment assigned at randomization. Because

Non-Invasive Treatment of Abdominal Aortic Aneurysm Clinical Trial

N-TA³CT

STATISTICAL ANALYSIS PLAN

treatment was never started and because the primary endpoint is not known and cannot be reasonably imputed in participants with no follow-up and no follow-up CT scan, analysis of the primary endpoint will be conducted on the *full analysis population*.

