8.1 Primary Efficacy Analysis

The primary analysis will be performed to test the null hypothesis of no difference in growth of abdominal aortic aneurysms between the two treatment groups (doxycycline and placebo) after 24 months of follow-up as measured by CT scans analyzed in the Imaging Core Laboratory. This analysis will use the full analysis population. In order to include patients whose 24-month abdominal CT scans are missing because of death, endovascular repair or for other reasons in the primary analysis, we will base our analysis on normal scores for percentile of rank status. We will assign worst ranks to deaths, in order of time from study entry to death, next worst ranks to rupture, next worst ranks to endovascular repair for clinical presentation, next worst ranks to endovascular repair for reasons of aneurysm growth beyond 5.5 cm in men or 5.0 cm in women or other presentation free of clinical indication, all in order of time from study entry within category. The order of ranks are summarized in Table 1. Clinical presentation will be assessed by the three vascular surgeon Principal Investigators, blinded to treatment assignment, independently; agreement by two of the three or all three will be taken as final. Outcomes for patients missing the 24-month CT scan will be imputed, as described in the next section.

Table 1. Summary of ranks.

Order of rank assignment (worst to best)	Description
1	Death (from day of study entry to day of death)
2	Aneurysm rupture (from day of study entry to day of repair)
3	Endovascular repair for reasons related to clinical presentation (from day of study entry to day of repair)

Non-Invasive Treatment of Abdominal Aortic Aneurysm Clinical Trial

N-TA³CT

STATISTICAL ANALYSIS PLAN

4	Endovascular repair for growth beyond 5.5 cm in men or 5.0 cm in women or other presentation free of clinical indication (from day of study entry to day of repair)
5	Change from baseline in largest, transverse diameter of the aneurysm, using normal scores as described below.

The ranks for patients assigned to doxycycline will be compared to the ranks of patients assigned to placebo using normal scores. If N is the total number of randomized patients, a rank of k will be assigned the value corresponding to $k/(N+1)$ in a standard normal distribution; for example, a rank of 100 out of 248 patients will receive the rank score corresponding to 0.4016, or a normal score $z = 0.2492$.

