The change in normal score from baseline -- i.e., the two-year normal score for patients randomized to doxycycline and placebo minus the baseline normal score -- will be analyzed using a linear regression model (analysis of covariance -- ANCOVA), with variables for the randomized treatment assignment (0 for placebo, 1 for doxycycline), the normal score for baseline diameter, and gender in the model.

Prior to performing the primary outcome analysis, an interaction term for the randomization stratum (gender) with treatment assignment will be assessed in the ANCOVA model. If there is significant (at two-sided $\alpha=0.05$) evidence of differences in the effect of treatment according to gender, other than a small quantitative difference (less than half a normal score difference in treatment effect) between effects that are in the same direction for each gender, the analysis will be performed separately for men and for women. In the event of a treatment by gender interaction being observed, we will review study results by gender to determine the nature of the differences in treatment effects. If there is no interaction, the ANCOVA will be used to estimate the overall treatment effects across all clinical sites and both strata (genders). The primary analysis will be performed on the normal scores corresponding to percentile rank of each patient at baseline and follow-up.

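### SAP 8.1 does not settle whether the two-year rank in the primary analysis is based on aneurysm growth or on 24-month diameter

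*SAP*

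**What the plan says.** Three places point to growth. Section 3.2 states: "The primary outcome is the change in abdominal aortic aneurysm maximum transverse diameter (MTD) on CT scan from baseline". Section 8.1 sets out to test the "null hypothesis of no difference in growth of abdominal aortic aneurysms between the two treatment groups". Row 5 of Table 1, the category for patients without an event, reads "Change from baseline in largest, transverse diameter of the aneurysm, using normal scores as described below".

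The model text later in 8.1 points to diameter. The dependent variable is "The change in normal score from baseline", spelled out as the two-year score minus the baseline score. The baseline-diameter score is also a covariate, and the analysis is "performed on the normal scores corresponding to percentile rank of each patient at baseline and follow-up".

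The scoring rule is: "If N is the total number of randomized patients, a rank of k will be assigned the value corresponding to" k/(N+1). The example takes rank 100 of 248 and prints z = 0.2492. The primary analysis, however, uses the full analysis population: "The full analysis population includes all patients randomized except those with no follow-up contact and no follow-up CT scan". Sections 8.2 and 8.3 apply the same method without imputation and to the per-protocol population.

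The gender-interaction rule in 8.1 tolerates a same-direction difference of "less than half a normal score difference in treatment effect". Section 4.2.2 makes the primary test one-sided at 0.0247.

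**The concern.** A change from baseline has no rank at baseline. A patient can have a percentile rank at both time points only if diameter is what is ranked. Read literally, row 5 ranks growth, and the model text then subtracts a baseline-diameter score from a growth score. Read the other way, row 5 is shorthand and growth, the defined outcome, is never ranked.

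Two competent programmers could therefore build different primary endpoints from this text. If the point is left open, the choice could be made after results are visible. The interaction tolerance also means a different number of millimetres on each scale, and it helps decide whether men and women are analysed separately.

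**Working it through.** **Inputs from the SAP.** N = 248, 1:1 allocation, growth 2.5 v 1.5 mm/year, 10% non-adherence on doxycycline, 15% missing two-year scans, power above 90% at one-sided 0.025 (sections 3.3.4 and 3.3.5); final one-sided level 0.0247 (4.2.2).

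**Design effect.** Over two years, placebo growth is 5.0 mm. Doxycycline growth is 0.9 × 3.0 + 0.1 × 5.0 = 3.2 mm, a difference of 1.8 mm.

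**Plan's power figure.** The SAP gives no SD, so the 90% cannot be reproduced, only inverted. With 0.85 × 124 = 105.4 per arm (about 211 in total), the largest SD giving 90% power is 1.8 / [(1.96 + 1.2816) × √(2/105.4)] = 4.03 mm. SDs of 3 to 4 mm were used.

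**Does subtracting the baseline score matter?** No. Let Y be the two-year score and B the baseline score. Y − B = a + b·treatment + c·B + d·gender is the same model as Y = a + b·treatment + (c + 1)·B + d·gender, so b and its t statistic are unchanged. In simulation the t values differed by about 1e-14. Only the variable behind Y matters.

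**Simulation.** There were 4000 trials per setting, so the standard error of a rejection rate is at most √(0.25/4000) = 0.8 points. Assumptions not in the SAP:
- SD 3.0, 3.5 or 4.0 mm; 85% men.
- Baseline uniform, or normal (mean 43, SD 4 mm) clipped to the eligible ranges.
- Deaths at random, taking the worst ranks.
- Repair when 24-month diameter passes 55 mm (men) or 50 mm (women), ordered by crossing time.
- No missing scans, so no imputation.

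Both versions used the same ANCOVA (treatment, baseline score, gender).

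| Events assumed | Power lost by ranking diameter (points) | Trials with different decisions |
|---|---|---|
| None | 0 to 1.1 | 0.1 to 2.2% |
| Diameter-driven repairs only | -0.3 to 0.4 | 0.3 to 3.6% |
| Repairs + 3% deaths | 2.5 to 7.0 | 2.7 to 9.0% |
| Repairs + 6% deaths | 8.6 to 13.4 | 8.6 to 13.9% |
| 5% deaths alone | 6.6 to 11.9 | 6.6 to 12.3% |
| 10% deaths alone | 13.7 to 21.9 | 14.9 to 22.0% |

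Type I error was 2.1 to 2.8% for both versions. A variant with non-adherence applied patient by patient (SD 4 mm, repairs plus 5% deaths) gave power of 84.0% for growth and 73.0% for diameter.

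Deaths drive the gap because the treatment effect is smaller in diameter-score units. A death's extreme score, unrelated to baseline, is therefore larger noise relative to the effect.

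**Half-score tolerance, no events.** In growth terms it is 0.5 × 1.8 / treatment coefficient. Absolute coefficients of 0.56 to 0.43 (growth ranked) give 0.9/0.56 = 1.6 mm to 0.9/0.43 = 2.1 mm. Coefficients of 0.36 to 0.31 (diameter ranked) give 0.9/0.36 = 2.5 mm to 0.9/0.31 = 2.9 mm. The design effect is 1.8 mm.

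**N in the scoring rule.** If 243 of 248 are ranked, the top score is z(243/249) = 1.98; if 236, z(236/249) = 1.62. With the correct denominator it is z(243/244) = 2.64 or z(236/237) = 2.63. The bottom score stays near -2.65, so one tail is cut. In 2500 trials per setting (growth ranked, SD 4 mm, 0 or 5% deaths), power changed by -1.3 to +2.4 points, and by -4.8 to +3.4 points with 211 ranked. The sign depends on rank direction.

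**Worked example.** 100/249 = 0.4016 reproduces, but z(0.4016) = -0.2492. The printed value belongs to the upper tail, 1 − 0.4016.

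**The case against.** The best counter-reading is that diameter is scored at each time point throughout. The model text spells out its dependent variable, names the baseline term as a score for diameter, and section 8.1.1 speaks of a score for the 24-month scan. Row 5 defers to what follows it and may be loose shorthand. A change in diameter score adjusted for baseline still bears on growth. On this view only a table row needs alignment, and telling the sponsor to rank change could override a protocol not seen here.

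That reading is possible, but the SAP never states it, and it conflicts with the literal Table 1 and is hard to square with the outcome in 3.2. Ranking change follows the SAP's own definition and loses no meaningful power in any setting examined. The protocol caveat is right and is carried into the fix.

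Other parts of the objection stand. The power figures rest on an SD, event rates and baseline distribution that the SAP does not give, and they omit imputation. Without deaths the versions almost agree. The N effect is small for the primary analysis. The sign error changes no analysis, and a minus lost in PDF extraction cannot be excluded. The direction of benefit can be inferred from the aim and from Table 1's worst-to-best order, and with N equal to the number ranked, reversing the ranks only flips the coefficient's sign.

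**Conclusion.** The concern holds. Section 8.1 supports two constructions of the primary endpoint and does not choose between them. The choice is close to immaterial if nobody dies. Under the stated assumptions it is worth 2.5 to 13.4 points of power with repairs plus 3 to 6% deaths, and up to 21.9 points with 10% deaths alone. Because Table 1 gives death the worst rank, the plan itself provides for the case in which the versions diverge. Type I error is not at risk once one version is fixed in advance; the exposure is a primary test that could be settled after the data are seen.

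The N definition and the sign of the example are wrong as printed but of small consequence. The unstated direction of benefit and the half-score scale are minor. This should be fixed before unblinding, but it does not undermine the design.

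**What to change.** In section 8.1:

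- State that the two-year score is the normal score of the Table 1 ranking, with row 5 ordered by change in MTD (observed or imputed), analysed with treatment, baseline-diameter score and gender as covariates. Reword the model text to match.
- Set N to the number of patients ranked in each analysis and in each imputed data set.
- Give one rank direction consistent with Table 1's numbering (rank 1 = worst, so benefit is a positive treatment coefficient), and rank baseline diameter the same way.
- Correct the example to z = -0.2492.
- State the score scale on which the half-score tolerance applies.

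If the protocol defines the score differently, record the change in section 8.4, which now lists only the renaming of the population, and say which version the interim analyses used.

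The cost is a few sentences before unblinding, plus possibly one entry in 8.4. No new data or design change is needed.

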8.1.1 Imputation for the Primary Efficacy Analysis

In the event a patient does not complete two years of CT scan follow-up for cause(s) other than death, rupture, open repair or endovascular repair (e.g., withdrawal of consent or loss to follow-up, expected to be infrequent events), the patient's previous CT scans and other characteristics will be used for the imputation of a measurement of the abdominal aortic aneurysm diameter to be included in the primary analysis. The model used for imputation will be developed as described below.

For the multiple imputation of missing 24-month CT scans, we first assume that event status is known for all participants. Therefore, we assume we are imputing the 24-month CT scan score only for patients who did not have an event. First, we will assess the 24-month CT scans of patients who did not have an event for normality and transform them if necessary. If the data

Non-Invasive Treatment of Abdominal Aortic Aneurysm Clinical Trial

N-TA³CT

STATISTICAL ANALYSIS PLAN

show egregious departures from normality, possible transformations are natural log transformations, square root transformations, or Box-Cox transformations. Second, we will model the MTD from the 24-month scan using fully conditional specification, a type of multiple imputation using chained equations (MICE), implemented with SAS 9.4's PROC MI under the FCS option. At a minimum, we will include MTD from the baseline CT scan, gender, treatment, and gender by treatment interaction, and MTD from CT scans obtained at 6-month, 12-month and 18-month follow-ups. The interaction of treatment by gender is included because the test of interaction is planned in the final analysis.

Additional variables that will be considered for the multiple imputation model are baseline history of coronary artery disease, peripheral vascular disease, cancer, chronic obstructive pulmonary disease, diabetes mellitus, hypercholesterolemia, baseline use of beta blockers, ACE inhibitors or angiotensin receptor blockers, calcium channel blockers, diuretics, non-steroidal anti-inflammatory drugs, use of aspirin or anti-platelet, adherence score, and current smoking status. Adherence scores over 100 will be censored to 100. A continuous variable will be added to the multiple imputation model if its Type III Wald Chi-Square test is significant at the 0.05 level in linear regression of the MTD from the 24-month CT scan after adjusting for baseline MTD, gender, treatment, and gender by treatment for complete cases. Alternatively, if a continuous variable's partial correlation with 24-month CT scan is above 0.4 or above $0.75* R^2$ after adjusting for baseline MTD, gender, treatment, and gender by treatment interaction, then it will be added to the multiple imputation model. The R^2 is the correlation of 24-month CT scan result with baseline MTD, gender, treatment and gender by treatment interaction.

To be considered for the imputation model, a categorical variable will be required to have at least 5 of each group in the data set. Any of the above listed categorical variables that is missing in 20% or more in the imputed cases will be excluded. If the final list of variables includes more than 3 different types of medications, the list will be sent to the Director for the Data Coordinating Center for a check of collinearity between variables on a biological basis. This information and consultation will in no way unblind the Director of the Data Coordinating Center to the results of the analyses. If there are collinear variables, only the variable with the higher partial correlation will be included in the modeling process.

Finally, using complete cases (i.e., cases with no missing values for the 24-month MTD or any of the candidate independent variables), we will start with a model for 24-month MTD that includes all the candidate independent variables and perform backward elimination to test whether or not there are variables that can be deleted. The initial model will include MTD from the baseline CT scan, 6-month scan, 12-month scan and 18-month scan, treatment, gender, treatment by gender variable, and any other variable that meets the above statistical requirements. Variables other than baseline MTD, gender, treatment and gender by treatment interaction will be included in the final imputation model if they have a p-value less than 0.05 after the backward elimination.

The process of choosing candidate variables and developing a final model for imputing 24-month MTDs will be implemented before each interim analysis of the primary endpoint, as well

Non-Invasive Treatment of Abdominal Aortic Aneurysm Clinical Trial

N-TA³CT

STATISTICAL ANALYSIS PLAN

as at the final analysis. Thus, variables that are used for the multiple imputation at one analysis may or may not be used at a different stage, as data on more participants are available.

Data from study participants who have a clinical endpoint event (death, rupture, or repair) before the 6-month follow-up CT scan will not be included in the fitting of the model for imputing the 24-month MTD for other participants. Data from participants who have an event after the earliest significant follow-up MTD will be included in the fitting of those models, but their rank for the primary analysis will be determined by the event they experienced – i.e., their data will be used in imputing the 24-month MTD for other participants, but their clinical event will be used in determining their rank in the primary analysis. Data from participants excluded from the multiple imputation modeling will be added back into the imputed data set, so that they will be included in the primary analysis.

In the imputation model, the MTDs from CT scans at 6, 12, and 18 months will be constrained to have a minimum value of 3.5 and a maximum value of 7, to reflect the plausible range of MTD's in participants who do not experience a clinical event. The maximum value for MTD's was purposefully set high in order to not constrain the within and between imputation variance. All imputed MTD values will be rounded to the nearest hundredth (0.01) to reflect the same accuracy as the observed values.

For the multiple imputation regression modeling, we will use the default SAS settings (linear regression for continuous variables, logistic regression for dichotomous variables, and discriminant function for nominal variables with more than 2 categories). Since we are using the default, there is no need to specify a method on the FCS statement of PROC MI. The default number of burn-in iterations of 10 will be used (NBITER=10). Variables other than final and intermediate follow-up MTDs will be listed on the VAR statement from most complete to least complete. MTDs from follow-up CT scans will be listed in chronological order, regardless of missingness, with MTD at 24 months listed last. A seed of 384830 will be used, and 100 imputed values will be created for each missing observation in the multiple imputation model.

The multiple imputation data set will be used to test the significance of both the treatment variable and the treatment by gender interaction. For both the test of the treatment by gender interaction and the subsequent test of treatment effect or treatment and treatment by gender interaction, the degrees of freedom will be adjusted. The adjusted degrees of freedom is a function of the complete-data degrees of freedom and the between-imputation and within-imputation variance estimates. In the test of treatment by gender interaction, the complete-data degrees of freedom is the number of subjects in the analysis minus one. If the test of interaction is not significant at the 0.05 level, then we test only the treatment effect and the complete data degrees of freedom is the same (number of subjects minus one). If the test of interaction is significant at the 0.05 level, then we test the treatment and treatment by gender interaction, and the complete-data degrees of freedom is the number of participants minus two, as we are estimating two parameters in this case.

Non-Invasive Treatment of Abdominal Aortic Aneurysm Clinical Trial

N-TA³CT

STATISTICAL ANALYSIS PLAN

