3.3.5 Sample Size and Power

The study is designed to have greater than 90% power with a total sample size of 248 patients for a one-sided 0.025 test for an assumed reduction of 40% in the mean increase in aneurysm diameter from 2.5 mm/year to 1.5 mm/year. The calculations allow for a 10% non-adherence rate in the doxycycline treatment group and for 15% of participants to have a missing two-year CT scans. Additional details regarding the sample size and power calculations are contained in the protocol.

4 General Consideration for Data Analyses

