4.2.2 Multiple Comparisons

For the primary analysis, we consider a one-sided p-value of 0.0247 to be significant. It is less than 0.025 to account for the interim analyses. To account for the multiplicity of hypotheses being tested in secondary and exploratory analyses, a p-value < 0.01 will be required to consider there to be evidence of differences present, i.e. to reject the null hypothesis. We consider p<0.001 as strong evidence.

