
8.2 Analysis *Without Imputation*

Using the same normal scores for percentiles of rank methodology described above (section 7.1), we will compare the treatment groups *without imputation of any missing 24-month CT measurements of the MTD of the aneurysm*.

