If we reject the null hypothesis with $\geq 40\%$ less growth in doxycycline group:

- An analysis without imputation will be performed. If the results of the analysis without imputation do not return an effect size similar to the primary outcome analysis, the rejection of the null hypothesis will be called into question as too highly dependent on imputation.
- Also, a per protocol analysis with an effect size similar to or larger than 40% would be supportive of the interpretation that a clinically significant effect was observed in the full analysis population, but if the per protocol analysis effect size were less than 40%, the clinical significance of the finding should be viewed as questionable.

If we reject the null hypothesis with a median growth less than 40% reduced in the doxycycline group as compared to the placebo group:

Non-Invasive Treatment of Abdominal Aortic Aneurysm Clinical Trial

N-TA³CT

STATISTICAL ANALYSIS PLAN

- Should the per protocol analysis be associated with an effect size greater than 40%, there could be reason for belief that a clinically significant benefit exists that would justify further investigation.
- Also, rejection of the null hypothesis with an effect size less than 40% but a large difference (e.g., doubling) of the proportion of patients whose aneurysms grew less than 1.0 mm or a large reduction (e.g., halving) of the proportion of patients whose aneurysms grew more than 6 mm would suggest the possibility of clinically significant benefit that would justify further investigation.

An alternative interpretation to be kept in mind whenever the null hypothesis is rejected is the occurrence of a difference by chance.

Failure to reject the null hypothesis:

Failure to reject the null hypothesis in the primary outcome analysis would be interpreted to mean that doxycycline did not have a beneficial effect size $\geq 40\%$ or that the design assumptions and performance were not of the quality necessary for a definitive test of the null hypothesis. If the effect size is $\geq 40\%$ but we do not reject the null hypothesis, we will examine the design assumptions and study performance carefully to report any deficiencies that may influence future investigations.

Non-Invasive Treatment of Abdominal Aortic Aneurysm Clinical Trial

N-TA³CT

STATISTICAL ANALYSIS PLAN

10 SAP Revision

Identify major changes. Only changes after sign-off need to be recorded.

Revision Date	Section	Summary of Revision	Reason for Revision

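### Section 9's test of dependence on imputation cannot detect informative loss: both analyses it compares assume ignorable missingness, so they can agree while both overstate the effect

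*SAP*

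**What the plan says.** Section 8.1 ranks deaths, ruptures and repairs worse than any change in diameter. Section 8.1.1 covers patients with no two-year scan for any other cause and gives as examples "withdrawal of consent or loss to follow-up, expected to be infrequent events". For the imputation it says "we first assume that event status is known for all participants", and it concludes that only event-free patients are being imputed. Every such patient therefore falls in the best category of Table 1.

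The imputation is fully conditional specification on observed data. Baseline diameter, gender, treatment, their interaction and the 6-, 12- and 18-month diameters are the stated minimum; adherence is one of the candidate variables. There is no delta term, no reference-based step and no draw of event status.

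Section 8.2 plans the same rank analysis "without imputation of any missing 24-month CT measurements of the MTD of the aneurysm". Section 9 gives that analysis its role. After a rejection with at least 40% less growth, if its effect size is not similar, "the rejection of the null hypothesis will be called into question as too highly dependent on imputation". No other check on dependence on imputation is named.

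**The concern.** For a patient who withdraws or is lost, freedom from events may be an assumption rather than an observation. If lost doxycycline patients lose the benefit of treatment, or have events that nobody records, the imputed analysis gives them ranks that are too good. The analysis without imputation drops them, which also assumes that the reason for loss carries no further information about outcome. The per-protocol population (section 4.1.3) requires a two-year scan or a recorded event, so it leaves them out too. No planned analysis can show the problem.

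At stake is how a positive result is read. Section 9 itself makes the investigators responsible for ruling out bias after a rejection, and agreement between the two analyses would look like reassurance on a question that neither addresses.

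**Working it through.** **1. The plan's own figure.** Section 3.3.5 claims "greater than 90% power with a total sample size of 248 patients for a one-sided 0.025 test". Its inputs are growth of 2.5 mm per year on placebo and 1.5 mm on doxycycline, with 10% of doxycycline patients non-adherent and 15% of two-year scans missing.

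- Difference over 24 months: 2 × (2.5 − 1.5) = 2.0 mm; with 10% non-adherence, 0.9 × 2.0 = 1.8 mm.
- Scanned patients per arm: 124 × 0.85 = 105.4.
- Power = Φ(1.8 / (SD × √(2/105.4)) − 1.96). The SAP gives no SD. SD 3.5 mm gives 96%, 4.0 mm gives 90.4% and 4.5 mm gives 83%; 90% is reached at SD 4.03 mm.

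The claim is consistent with an SD up to about 4.03 mm and no error is shown. An SD of about 4 mm is therefore assumed below.

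**2. How many patients.** 15% × 248 = 37.2, about 37 missing scans. The SAP does not split these by cause, so 37 is an upper figure for those imputed.

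**3. What each analysis needs.** The imputed analysis needs missingness unrelated to the 24-month outcome given baseline, treatment, gender and earlier scans, and no hidden events. The unimputed analysis needs missingness unrelated to outcome given baseline, treatment and gender alone. It implicitly gives lost patients the event mix of retained patients. What the two share is ignorability; the second needs a stricter form of it.

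**4. Lost doxycycline patients growing as placebo.** Simulation with 400 trials, 10 imputations, interim scans in the imputation model and uniform dropout time. Loss and event rates are assumed. Effects are normal-score ANCOVA coefficients (negative favours doxycycline); overstatement = estimate / full-data value − 1.

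- Loss 10%/10%, placebo-rate growth from randomisation: full data −0.339, imputed −0.356, unimputed −0.373. Overstatement 0.017/0.339 = 5% and 0.034/0.339 = 10%.
- Loss 5% placebo/15% doxycycline, same growth: imputed analysis overstates by about 10%.
- Placebo-rate growth only after last contact: about 8% (10%/10%) and 16% (5%/15%).
- With 20% hidden events among the lost, at 5%/15% loss: above 20%.

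Across such settings the overstatement was about 5-27% with imputation and 8-31% without, and the two analyses differed by only about 0.002-0.02.

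**5. Stronger informative loss.** A separate simulation: N = 248, 180 trials per row, 20 imputations, about 13% lost, about 10% observed events, one-sided 0.0247 (section 4.2.2).

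| Scenario | Full data | Imputed | Unimputed |
|---|---|---|---|
| No growth effect; hidden events in 5% of lost placebo, 50% of lost doxycycline patients | +0.109 | +0.009 | +0.007 |
| 1.0 mm growth effect; same hidden events | −0.065 | −0.181 | −0.176 |
| 1.0 mm growth effect; lost doxycycline patients 6 mm larger than predicted | −0.043 | −0.189 | −0.182 |
| Extreme bound: no growth effect; events in all lost doxycycline, no lost placebo patients | +0.243 | +0.008 | +0.005 |

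In each row the planned analyses lie within 0.007 of each other while both miss the full-data value by 0.10-0.24. In rows 2 and 3 rejection rises from 7% on full data to 26% and 29% imputed, and to 23% and 26% unimputed.

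With hidden events equal at 30% in both arms and a 1.8 mm effect, the values were −0.313, −0.341 and −0.326. Overstatement is then 0.028/0.313 = 9% imputed and 0.013/0.313 = 4% unimputed. Imbalance between arms drives the larger figures.

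**6. The opposite failure.** With no effect and loss depending on the 6-month scan, the imputed estimates were −0.006 and −0.003 (essentially unbiased), and the unimputed ones −0.120 and −0.236. These runs show the two diverging while imputation is right. They are null runs, so they illustrate the divergence rather than an actual rejection put in doubt.

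**The case against.** - **The planned imputation is better than a crude one.** It uses the patient's own earlier scans, so a lost patient already growing at the placebo rate shows it. This stands. A model without those scans overstated by about 13% at 10%/10% loss, against 5% with them. A reader might infer that lost doxycycline patients are imputed as if fully benefiting; the specified model does not support that. Earlier scans do not help when growth changes after last contact or an event goes unseen.
- **The comparison does what it says.** It asks whether the result depends on imputation, does not claim to test informative loss, and only calls a rejection into question. This is fair, but a rule meant to guard a positive result against reliance on imputation should address the assumption that imputation rests on.
- **Event status may in fact be known.** Missing scans are not all lost patients, section 3.3.3 allows some telephone visits, and the protocol, not shown, may provide for vital-status follow-up. That would reduce hidden deaths, but not unseen growth.
- **Little threat under the null.** If lost doxycycline patients simply grow as placebo there is no null bias. With 5%/15% loss and 20% hidden events the shift is about 0.04, against a standard error near 0.12. This stands.

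**Conclusion.** The point holds as a weakness of the section 9 safeguard, not of the primary method. No planned analysis allows for informative loss, and the one named check can reassure wrongly or diverge when the imputed result is sound.

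Overstatement by the imputed analysis is roughly 5-16% if lost doxycycline patients grow at the placebo rate. It is above 20% if, in addition, 20% of lost patients had unseen events and loss is 5% placebo/15% doxycycline. These sizes are illustrative: the SD (about 4 mm), loss rates and hidden-event rates are assumptions.

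Two stronger readings are tempting and not supported. One is that the two analyses make the same assumption and so must agree; their assumptions differ in strength and they can diverge widely. The other is that a positive result would probably be false; bias under the null is small unless hidden events differ strongly by arm. The change should be made before unblinding, because a rule chosen afterwards would carry little weight.

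**What to change.** Keep the primary multiple imputation. In section 9, base the dependence-on-imputation rule on a prespecified missing-not-at-random analysis with two parts:

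1. Reference-based imputation: lost doxycycline patients imputed from the placebo-arm model after last contact.
2. An arm-specific tipping-point (delta) analysis that also lets a varying share of patients with unknown event status, in both arms, take event ranks.

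The second part is needed because the first does not address hidden events. In a simulation without interim scans, with 5%/15% loss and 20% hidden events, reference-based imputation gave −0.319 against a full-data −0.272, still 17% too large (0.047/0.272).

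Keep the analysis without imputation as descriptive. Ranking every lost doxycycline patient, and no lost placebo patient, as a Table 1 category 4 event is not advised: in simulation it moved a null effect to +0.161 and a true −0.337 to −0.170.

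The cost is a SAP paragraph, one or two extra multiple-imputation runs on existing data, and a somewhat less favourable sensitivity estimate.
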